#### 6.6.4 Definition of Maximum Tolerated Dose

The MTD will be selected from all tried dose levels that have not been previously declared to be unsafe with a DU decision according to the mTPI-2 algorithm. With this constraint, the MTD will be determined as the dose level with the DLT estimate closest to the target toxicity level of 30%.

In the case of dose levels with estimated toxicity of equal distance (tied dose levels) from the target toxicity of 30%, the following approach will be used (Ji et al, 2010): among all tied dose levels the highest dose level with target toxicity  $\leq$  30% will be selected, unless all tied dose levels have estimated toxicity  $\geq$  30%, in which case the lowest dose level will be selected.

## 6.6.5 Definition of Optimal Biological Dose

The OBD will be determined from the safety, efficacy, PK, pharmacodynamic, and biomarker data during the dose escalation phase. The RP2D will be selected by AstraZeneca in discussion with the members of the Study Steering Committee, based on the totality of the data from the dose escalation phase of the study.

Pharmacokinetic and pharmacodynamic data collected in Parts A and B will provide demonstration of adequate drug exposure and high target binding level. Data demonstrate that clinical efficacy of the approved anti-PD-1 agents, pembrolizumab and nivolumab, is associated with PD-1 receptor occupancy (RO) > 90%, thereby suggesting that a similar level of PD-1 inhibition by sabestomig will confer clinical benefit at least equivalent to that of pembrolizumab and nivolumab.

## 6.6.6 Definition of DLT-evaluable Participants

For decisions on dose escalation, an evaluable participant is defined as a participant who has received sabestomig and has completed the DLT period (28 days after receiving 1st dose of sabestomig) or has experienced a DLT during the DLT period.

## 6.6.7 Safety Review Committee

To ensure safety surveillance of developmental compounds in line with regulatory expectations for safety assessment committees, AstraZeneca has systematic and robust internal processes in place. This includes processes with clearly described roles and responsibilities that are owned by AstraZeneca's Patient Safety organization. These processes are designed to monitor the evolving safety profile (ie, review of cumulative SAEs, or other important safety information) by designated cross-functional teams in a timely manner at predefined intervals or on an ad-hoc basis.

In addition to AstraZeneca's internal processes, a study-specific SRC, in accordance with its charter, will provide ongoing safety surveillance of the study, with regularly scheduled reviews of safety, PK, and other relevant data. The SRC comprises of members of AstraZeneca and investigators. This committee may also meet to review data at other time points (eg, in response to AEs assessed as medically relevant by the Study Physician). This committee will be responsible for making recommendations for dose escalation or dose deescalation decisions and making recommendations regarding further conduct of the study during all phases of the study including suspension or stopping of the trial. The SRC will review the totality of all available clinical, laboratory safety and all other relevant data prior to adjudicating on dose escalation/de-escalation decisions based on the dose escalation rules. All decisions by this committee will be documented and shared in writing with all participating sites.

During Part A, in addition to continuous monitoring as per AstraZeneca pharmacovigilance process, the SRC will evaluate toxicities occurring study wide. In addition, to assess potential late toxicity occurring beyond the DLT window, an analysis of cumulative safety data will be performed and shared with the SRC when 1) once at least 6 participants have completed at least 2 cycles of study drug, and 2) after completion of Part A (Dose Escalation) and prior to moving to Part B (Dose Expansion).

The membership, roles, responsibilities, and decision-making process will be detailed in the SRC charter.

#### 6.6.8 Dose Modification and Toxicity Management

If a participant experiences a clinically significant and/or unacceptable toxicity including a DLT not attributable to the disease or disease-related processes under investigation, dosing will be interrupted, and supportive therapy will be administered.

All toxicities will be graded according to NCI CTCAE v5.0.

The following general guidance should be followed for management of toxicities:

- Treat each of the toxicities with maximum supportive care (including withholding the agent suspected of causing the toxicity if required).
- If the symptoms promptly resolve with supportive care, consideration should be given to resuming the assigned study intervention along with appropriate continuing supportive care. If medically appropriate, dose modifications (eg, dose interruption) are permitted.
- All dose modifications (eg, dose interruption, discontinuation) should be documented with clear reasoning and documentation of the approach taken.
- Dose reductions are not permitted.

Toxicity Management Guidelines have been developed to assist Investigators with the recognition and management of toxicities associated with use of the IC inhibitor sabestomig. The TMGs are provided in Appendix I.

These TMGs are applicable to the management of participants receiving sabestomig as specified in the CSP. The TMGs provide information for the management of immune-mediated reactions, IRRs, and non-immune-mediated reactions that may be observed with monotherapy or combination checkpoint inhibitor regimens, with specific instructions for checkpoint inhibitor-specific dose modifications (including permanent discontinuation) and treatment interventions. Investigators are advised however to use local practice guidelines and consult local references for the management of toxicities observed with other anticancer treatment.

## 6.7 Dose Delay

In the event of treatment-related toxicities, study intervention should be permanently discontinued if sabestomig is not given for more than 12 weeks.

If treatment interruption is caused by intercurrent illness that is not a direct consequence of sabestomig-related toxicity (ie, COVID-19 infection), the option to restart treatment can be offered beyond 12 weeks following discussion with the AstraZeneca representative. In the event of a COVID-19 infection, the investigator should use their judgment to delay treatment with sabestomig depending on the clinical situation of the participant.

## 6.8 Treatment Beyond Progression

Participants may continue to be treated with the scheduled regimen and dose assigned at the discretion of the Investigator until one of the following criteria is met:

- Disease progression based on the Modified Lugano criteria assessed by the Investigator or pathological progression confirmed by biopsy. The assessment of PD must be confirmed by a repeat evaluation made by PET.
- Any of the study intervention discontinuation criteria is met.
- Clinical symptoms or signs indicating clinically significant PD such that the benefit-risk ratio of continuing therapy is no longer justified based on Investigator judgment.
- Decline in ECOG performance status compared to baseline.
- Rapid PD or threat to vital organs/critical anatomical sites (eg, spinal cord compression) requiring urgent alternative medical intervention, and/or continuation of study therapy would prevent institution of such intervention.

## Pseudo progression:

During immunomodulatory agent therapy (eg, checkpoint inhibitors, BTK inhibitors, CAR T-cell therapy, bi-specific antibody, lenalidomide, brentuximab-vedotin), imaging findings suggestive of PD without clinical deterioration may instead represent a tumor flare (also called pseudo-progression). To avoid early termination of the study treatment, if a pseudo-progression is suspected (eg, in presence of tumor flare with no clinical deterioration), it is recommended that a lymph node biopsy (if applicable) and a subsequent imaging at least 4 weeks apart from the initial assessment (and within a maximum of 12 weeks) is done, to confirm true PD versus a tumor flare/pseudo-progression.

# 6.9 Continued Access to Study Intervention After the End of the Study

AstraZeneca will continue to supply sabestomig in the continued access phase of the study (ie, PTAP), if the participant consents to this, and while in the opinion of the investigator and in agreement with the medical monitor, the participant is benefiting from the treatment.

Treatment will continue until PD occurs as judged by the investigator, completion of a participant's current 35-cycle treatment period, or until meeting any other discontinuation criteria defined in Section 7.1. Participants should be followed according to the institution's SoC assessments and as deemed appropriate by the investigators. It is recommended that investigators continue to observe ongoing participants at the frequency employed prior to the final DCO. No further data collection is required, except for safety reporting. The investigator and any designees are responsible for detecting, documenting, and recording events that meet the definition of AE and SAE and special situations (see Sections 8.3, 8.4, and Appendix D). Adverse events will be collected from time of signature of ICF throughout the PTAP until 90 days after the last dose of sabestomig, regardless of whether the participant has initiated a new anticancer treatment.

Protocol dose modification and stopping criteria are to be followed while a participant is receiving sabestomig. A change in the dose/schedule of sabestomig should only occur for safety reasons, based on the investigator's judgment, and should follow the approach for dose reduction and discontinuation as described in this protocol.

In the event that product development reaches a point where alternative product supply options become available, then these alternative product supply options will be discussed by AstraZeneca with the investigator. AstraZeneca will work with the investigator to transition the participant(s) to alternative supply, where possible. In the event that AstraZeneca terminates further development of the study intervention, AstraZeneca will continue to supply study intervention where possible, however the supply may become unavailable. AstraZeneca will notify investigators in advance if supply of study intervention must be discontinued.

In the event that a rollover or safety extension study is available at the time of the final DCO and database closure, participant(s) currently receiving treatment with sabestomig may be transitioned to such a study, and the current study would reach its end. The rollover or safety extension study would ensure treatment continuation with visits and assessments per its protocol, as applicable. Any participant who would be proposed to move to such a study would be asked to sign a new ICF, as applicable.

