#### **Intervention Groups and Duration:**

Following an initial screening period of up to 4 weeks, eligible participants will receive sabestomig every 3 weeks (Q3W) administered via intravenous infusion at the selected dose starting on Cycle 1 Day 1. Participants will be treated with study intervention for a maximum of 35 cycles, or until disease progression, unacceptable toxicity, withdrawal of consent, or if other reasons to discontinue treatment occur. All participants will be followed for survival until the end of study, regardless of whether treatment was discontinued.

No dose reductions of sabestomig will be allowed. Dose modification (hold or delay) and toxicity management for sabestomig-related toxicity, including management of immune-mediated reactions, infusion-related reactions, and non-immune-mediated reactions are provided in the Toxicity Management Guidelines (Appendix I).

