## 6.10 Treatment of Overdose

For this study, any dose of study intervention in excess of that specified in this CSP will be considered an overdose.

In the event of an overdose, the Investigator should:

• Evaluate the participant to determine, in consultation with the Study Clinical Lead, if possible, whether study intervention should be interrupted or whether the dose should be reduced.

- Closely monitor the participant for any AE/SAE and laboratory abnormalities as medically appropriate and at least until the next scheduled follow-up. Refer to Section 8.4 for details of AE/SAE reporting related to overdose.
- Obtain a plasma sample for PK analysis if requested by the Study Clinical Lead (determined on a case-by-case basis) on day of visit (after end of infusion) if no other PK samples are scheduled; alternatively, up to 3 days from the date of the last dose of study intervention.
- Document the quantity of the excess dose as well as the duration of the overdose.

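### The protocol forbids any reduction of the sabestomig dose, yet Section 6.10 offers one after an overdose and Section 6.9 points to a reduction procedure that the protocol does not contain

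*Protocol*

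**What the plan says.** Two places in the protocol prohibit dose reduction:

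- **Synopsis, Intervention Groups and Duration:** "No dose reductions of sabestomig will be allowed". The next sentence limits what may be modified: "Dose modification (hold or delay) and toxicity management for sabestomig-related toxicity" is referred to Appendix I.
- **Section 6.6.8:** "Dose reductions are not permitted". The same section gives its examples of modification as follows: "All dose modifications (eg, dose interruption, discontinuation) should be documented".

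Two places treat reduction as available or as described:

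- **Section 6.9 (continued access):** "A change in the dose/schedule of sabestomig should only occur for safety reasons, based on the investigator's judgment", and such a change "should follow the approach for dose reduction and discontinuation as described in this protocol". The sentence before reads "Protocol dose modification and stopping criteria are to be followed while a participant is receiving sabestomig".
- **Section 6.10 (overdose):** the investigator is to determine, consulting the Study Clinical Lead if possible, "whether study intervention should be interrupted or whether the dose should be reduced".

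Section 9.4.3.2, on adverse event analysis, also names dose reduction among examples of interventions that may mark an event as significant. That is a reporting example and not a dosing instruction.

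**The concern.** A site that turns to Section 6.9 or 6.10 does so because a participant has a safety problem or has received too much drug. At that moment the text should give one answer. Section 6.10 names reduction as an alternative to interruption, while Section 6.6.8 excludes it. Section 6.9 sends the reader to a reduction procedure; the reader who goes looking finds a ban and no steps.

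What is at stake is consistent handling of an investigational product across sites. One investigator could lower a dose on the strength of 6.10, and another could refuse on the strength of 6.6.8, and both could cite the protocol. The matter is not confined to the period after the final data cut-off, because Section 6.10 applies during the main study. In the access programme, participants are still dosed and safety reporting continues.

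**Working it through.** No arithmetic applies. The check sets side by side the passages that bear on changing a participant's dose.

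**1. Is the prohibition qualified anywhere?** No. Neither the Synopsis nor Section 6.6.8 makes an exception for overdose or for continued access.

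**2. Does a reduction procedure exist for Section 6.9 to point to?**

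| Place | Measures it provides |
|---|---|
| Synopsis | Hold or delay |
| Section 6.6.8 | Interruption, discontinuation |
| Section 6.7 | Delay, with a rule on when a delay becomes permanent discontinuation |
| Appendix I | Hold, resume, discontinue; for infusion reactions, slow or interrupt the infusion |
| Section 6.6.1.2 | De-escalation between dose-level cohorts during dose finding |

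Slowing an infusion changes the rate and not the dose. De-escalation under the mTPI-2 rule decides the level at which further participants are treated; it does not lower the dose of someone already on treatment. None of these is the approach that 6.9 refers to, so the reference has no target.

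**3. What does Section 6.9 instruct?** It orders no reduction. It restricts changes to safety reasons and keeps the protocol's own modification criteria in force. A change of schedule under 6.9 agrees with the rest of the protocol, since delay is provided for. Only the words on dose reduction have nothing behind them.

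**4. What does Section 6.10 instruct?** It puts reduction to the investigator as a decision to be made. Two readings are open. If reduced means below the assigned dose, the section contradicts 6.6.8 and the Synopsis. If it means back down to the assigned dose after an excess, there is no contradiction. The text does not say which.

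**5. Would a reduction damage the planned analyses?** SAP Section 4.5.1.1 defines relative dose intensity as RDI = 100% × d/D, where d is the cumulative dose actually delivered and D the cumulative dose intended with no modification of dose or schedule. A reduction lowers d and leaves D unchanged, so RDI falls; the definition still works. Protocol Section 9.3 and SAP Section 3.2 classify participants by assigned dose for efficacy, and by dose actually received for safety and PK. A reduction would not move anyone between efficacy groups. After the final data cut-off, Section 6.9 requires only safety reporting, so no efficacy or dose-intensity analysis draws on the access programme. SAP Section 4.5.1.2 summarises dosing deviations for treatment cycle delays only. A reduction would therefore have no reason category there, which fits a plan that expects none.

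**The case against.** The strongest reply has four parts.

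- **Section 6.9 defers to the protocol.** It says that the protocol's modification criteria apply, so a site that follows the reference ends at the prohibition. This stands in part: 6.9 gives no permission to reduce, and a reader who infers that it tells sites to lower the dose goes further than the text. It remains a reference to something absent and forbidden, in a section written for participants who are still being dosed.
- **Section 6.10 is narrow and may be harmless.** It covers one event, foresees consultation with the Study Clinical Lead, and may mean only a return to the assigned dose. The version history in Appendix L describes the overdose text as a standard-text update, which suggests generic wording. These points lower the chance of divergent handling. They do not settle the meaning, and the consultation is qualified by if possible.
- **Overdose should be uncommon.** Under Section 6.4 a second staff member confirms the dose at each administration. That is a fair limit on frequency, although the documents give no figure.
- **The analyses survive.** A reader might infer that a reduction would invalidate relative dose intensity or the analyses at the recommended Phase 2 dose. The documents do not support this: the d/D ratio accommodates a lower dose, and efficacy grouping follows the assigned dose.

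**Conclusion.** The inconsistency is real and lies in current, unredacted operative text. For Section 6.10 it is an apparent direct conflict with Section 6.6.8 and the Synopsis, and it becomes an actual one if reduced means below the assigned dose. For Section 6.9 it is a dead pointer to a prohibited procedure. To describe all four places as giving opposite dosing instructions would overstate the position for 6.9.

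The size is modest: on-study overdoses and safety-driven dose changes in the access programme, with no frequency stated for either. It does not extend to every safety event in that programme, because the hold and discontinue rules of Appendix I continue to apply there. The consequence is possible inconsistency between sites in handling a participant, and not a biased estimate. The conclusion rests on no protocol section other than those compared here describing a within-participant reduction. It takes no position on whether reductions should be allowed.

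**What to change.** Reconcile the Synopsis, Section 6.6.8, Section 6.9 and Section 6.10 so that all four give the same instruction on dose reduction. The sponsor decides which rule applies.

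- If the prohibition stays, Section 6.9 should stop referring to a reduction approach, and Section 6.10 should drop the option or state what reduced means there.
- If reduction is to be possible in either setting, the procedure has to be written down and the Synopsis and Section 6.6.8 changed to match.
- In either case, align the mention of dose reduction in Section 9.4.3.2 with the rule chosen.

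The cost is a few sentences at the next protocol amendment. If the prohibition stays, no SAP change is needed. If reduction is allowed on study, the dosing-deviation summary in SAP Section 4.5.1.2 would need a category for it.

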## 6.10 Treatment of Overdose

For this study, any dose of study intervention in excess of that specified in this CSP will be considered an overdose.

In the event of an overdose, the Investigator should:

• Evaluate the participant to determine, in consultation with the Study Clinical Lead, if possible, whether study intervention should be interrupted or whether the dose should be reduced.

- Closely monitor the participant for any AE/SAE and laboratory abnormalities as medically appropriate and at least until the next scheduled follow-up. Refer to Section 8.4 for details of AE/SAE reporting related to overdose.
- Obtain a plasma sample for PK analysis if requested by the Study Clinical Lead (determined on a case-by-case basis) on day of visit (after end of infusion) if no other PK samples are scheduled; alternatively, up to 3 days from the date of the last dose of study intervention.
- Document the quantity of the excess dose as well as the duration of the overdose.

## 7. DISCONTINUATION OF STUDY INTERVENTION AND PARTICIPANT DISCONTINUATION/WITHDRAWAL

## 7.1 Discontinuation of Study Intervention

It may be necessary for a participant to permanently discontinue (definitive discontinuation) study drug. Note that discontinuation from study drug is NOT the same thing as discontinuation from the study.

Participants may be discontinued from study drug in the following situations:

- Confirmed disease progression by PET-CT.
- An AE that meets criteria for discontinuation of study drug (as defined in Sections 6.6.3 and 6.6.8 and the Toxicity Management Guidelines, Appendix I) or in the opinion of the Investigator or AstraZeneca warrants discontinuation of further dosing.
- Investigator determination that the participant is no longer benefiting from study intervention.
- Participant decision. The participant is at any time free to discontinue treatment, without prejudice to further treatment.
- Pregnancy or intent to become pregnant (Section 8.3.10).
- Non-compliance with the CSP (Investigator or participant).
- Participant incorrectly initiated on study intervention.
  - When the reason does not impact safety consider the risk/benefit to the participant of stopping treatment.
- Unexpected, significant, or unacceptable risk to the participants enrolled in the study.
- AstraZeneca termination of study for reasons including but not limited to unfavorable risk/benefit or change in drug development plan.

If study drug is permanently discontinued, the participant will remain on study to be evaluated for protocol-specified assessments including follow-up of any AEs and survival follow-up. At the time of study drug discontinuation, the participant will be followed-up for safety and a visit will be performed 30 and 90 days after receiving the last dose of sabestomig.

